Several score systems have been proposed in order to intraoperatively stratify patients based on their risk of developing POPF, allowing a risk-adjusted approach to the reconstructive phase of PD.^{1,2} The fistula risk score (FRS) is the most used and extensively validated, and it is based on predictors such as pancreatic parenchyma texture, presumed pathology, main pancreatic duct diameter and estimated intraoperative blood loss (EBL). This prognostic score is able to identify a high-risk cohort (FRS 7-10) representing about 10% of all PDs and having an increased rate of POPF (around 30% and up to 40% in the FRS 10 patients) and consequently worse postoperative outcomes with a major postoperative morbidity around 35%.^{3,4} Recently, a large multi-institutional retrospective study and a randomized controlled trial both identified an optimal combination of therapeutic strategies able to mitigate the incidence and the burden of POPF in high-risk patients. Those “mitigation strategies” were the use of externalized trans-anastomotic stent (ETS), pancreatico-jejunal anastomosis (PJ), drains placement and the omission of prophylactic octreotide.^{4,5} However, both morbidity and mortality rates after high-risk PD (HR-PD) remain extremely high, even after the implementation of the above-mentioned strategies.⁵ Due to its clinical burden, POPF is still associated with delays (> 8 weeks) or omission of adjuvant therapy in two-thirds of complication-bearing patient.⁴

Given the increased postoperative burden of high-risk PDs, total pancreatectomy (TP) might be advocated for those who are at a high-risk for POPF, especially after recent studies showing improved postoperative outcomes of TP at high-volume centers. Stoop et al. found that the historic major postoperative morbidity of 34% after TP decreases to 23% when considering only the most recent years, similarly to another bicentric study including patients undergoing TP from 2000 to 2014.^{6,7} A more recent multicenter snapshot study, including TP performed at both high- and low- volume centers between 2018 and 2019, showed a major morbidity of 25% and an in-hospital mortality of 5%.⁸ Moreover, recent studies have reported improved postoperative quality of life (QoL) after TP compared to the past, presumably due to centralization at high-volume centers and development of long-acting insulin and modern pancreatic enzyme preparations.^{6,9,10,7}

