- To evaluate the access to adjuvant chemotherapy (when indicated)
- To evaluate cancer-specific, pancreas-specific, and diabetes-related QoL in each group

MATERIAL AND METHODS

The study will be organized as a multicentric randomized controlled trial. When a patient will be considered eligible preoperatively, he or she will be enrolled in the present study.

The patient's risk will be allocated intraoperatively after the demolitive time and before pancreatic anastomosis, according to the following criteria:

Major Criteria
Main pancreatic duct diameter $\leq 3\text{mm}$
Soft pancreas
Minor Criteria
Bleeding stump
Friable stump
Posterior/Eccentric duct
Invisible duct
Deep pancreas
Intraoperative acute pancreatitis
FRS 9-10
Interobserver agreement
≥ 2 Surgeons

Table 1 Eligible patients will have two major and one or more minor criteria confirmed by at least two surgeons

Patients presenting with all major criteria (stage D according to Schuh et al.¹²) and at least one among the minor criteria will be considered eligible. At least two surgeons must confirm eligibility, according to interobserver agreement regarding the above-mentioned criteria and ethical applicability of randomization (ethical “guarantor”). Eligible patients will be randomized to receive PA or TP.

Pre-operative, intra-operative and post-operative data will be recorded prospectively by the P.I. and by his collaborators.

Population

Inclusion criteria

Preoperative

- Patients older than 18 years
- All patients scheduled for PD for all kind of pancreatic diseases
- Patients able to give their informed consent

Intraoperative

- Patients undergoing PD (Kausch-Whipple or Longmire-Traverso)
- Patients presenting two major and at least one minor criteria (Table 1)
- Two or more surgeons confirming eligibility
- PA or TP with or without spleen preservation (Kimura technique). These techniques are consistent with clinical practice; any other procedure will be a deviation from the protocol

Surgical techniques different from those mentioned in the section “procedures” will be considered as a violation of the current protocol.

Drop-out criteria

Preoperative

- Informed consent withdrawal
- Impossibility to undergo surgery for any reason
- Main pancreatic duct of the pancreatic neck/body >3mm at preoperative imaging (CT scan or MRI)

Intraoperative

- PD not performed for any reason
- Absence of two major criteria

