each Institution's standards of care. In the PJ Group, the amylase value of drain fluids will be checked on POD1, POD3 and at any POD if it will help to diagnose a still undiscovered POPF. Surgical drain will be managed according to clinical judgment and each Institution's clinical standards. During hospitalization, all patients will receive specialistic evaluation to assess and possibly treat the occurrence of new onset diabetes or the worsening of pre-existing diabetes. Pancreatic exocrine insufficiency will be treated with oral supplementation of pancreatic enzymes if needed. Patients in the TP Group will be vaccinated 1 month after complete functional recovery against Pneumococcus, Hemophilus influenzae group B, and Meningococcus to minimize the likelihood of developing post-splenectomy sepsis. All patients will receive an outpatient follow-up, 1 month after discharge and every 6 months for 2 years. During follow-up, glycemic control, nutritional status, and possible symptoms of exocrine insufficiency will be assessed, and patients will receive specialistic assistance if needed. QoL will be registered using specific questionnaires. An oncologic evaluation will determine the indication for administration of adjuvant therapy, in case of malignancy.

Questionnaires

All patients who will be alive after at least 12 months of follow-up will be enrolled in the cross-sectional study of quality of life. All the eligible patients who are not able to attend outpatient visits will be contacted by telephone before receiving the 5 questionnaires by mail. Patients who will not respond within 1 month will be contacted again by telephone. Four questionnaires will be administered: (1) the EuroQoL Group questionnaire (EQ-5D); (2) the European Organization for Research and Treatment of Cancer (EORTC) QLQ-C30 questionnaire; (3) the European Organization for Research and Treatment of Cancer (EORTC) QLQ-PAN26 questionnaire; and (4) the Problem Areas in Diabetes (PAID) questionnaire.^{17 18 19 20} The comprehensive assessment will consist of a total of 116 questions.

ENDPOINTS

Primary endpoint

For each study group the primary endpoint is the rate of postoperative major morbidity, defined as Clavien-Dindo ≥ 3 .

Secondary endpoints

For each study group secondary endpoints are:

- Incidence of In-hospital, 30-days and 90-days postoperative mortality. Beyond these time-limits, the mortality that may be related to the operation will be considered and discussed in each case.

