- Incidence, severity, and overall average complication burden for PPH and DGE
- Incidence of other postoperative morbidity (see below)
- Time-to-functional recovery (functional recovery is defined by all of the following criteria: adequate pain control with only oral analgesia (no intravenous or epidural analgesia necessary); independent mobility; ability to maintain more than 50% of the daily required caloric intake; no need for intravenous fluid administration; and no signs of infection)²¹
- Length of hospital stay
- Postoperative endocrine insufficiency (new onset diabetes, worsening of pre-existent diabetes, insulin dependency). The definition of postoperative new onset of diabetes will be based on the reporting of a normal preoperative FBG/HbA1c and postoperatively by measured glucose metabolism including FBG/HbA1c level and/or insulin medication.
- Postoperative exocrine insufficiency (incidence of diarrhea, prescription of pancreatic enzymes, number of capsules). The definition of postoperative exocrine insufficiency will be based on FE-1

determination, the presence of steatorrhea and necessity of enzyme treatment with cessation/mitigation of diarrhea after enzyme supplementation.

- Access to adjuvant chemotherapy (when indicated)
- Delay in starting adjuvant chemotherapy, calculated as the time between surgery and the beginning of adjuvant chemotherapy (when indicated)
- General, cancer-specific, pancreas-specific and diabetes-related QoL (EQ-5D; EORTC QLQ C30 and PAN26; PAID) ^{17 18 19 20}

The observation period for postoperative morbidity will last until the complete recovery from surgery.

Morbidity will include:

- PPH as defined by ISGPS ²²
- DGE as defined by ISGPS ²³
- Bile leakage as defined by ISGLS²⁴
- Enteric fistula defined as presence of enteric fluid from drains, possibly confirmed by sinogram or plain radiography with oral contrast study
- Abdominal fluid collection defined as any intraabdominal fluid collections larger than 5cm confirmed at imaging
- Abdominal abscess defined as an intraabdominal fluid collection containing gas bubbles and producing clinically relevant signs of infection
- Wound infection as defined by CDC ²⁵
- Blood transfusions defined as the number of packed red blood cells unit transfused after the procedure
- Sepsis ²⁶
- Chyle leak as defined by ISGPS ²⁷
- Gastric venous congestion ¹⁶
- Postoperative liver failure
- Myocardial infarction
- Acute kidney injury
- Pulmonary embolism
- Pneumonia

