- Respiratory distress (defined as the need for mechanic ventilation after surgery)
- Urinary tract infection
- Neurological morbidity (cerebrovascular accidents, hemorrhage)
- Re-operation
- Re-admission within 30, 60 and 90 days

For PA Group additional secondary endpoints are:

- Incidence and severity of POPF ²⁸
- Incidence of biochemical leak ²⁸
- Overall average complication burden for POPF
- Incidence of postoperative pancreatitis ²⁹

SAMPLE SIZE CALCULATION

A recent metanalysis by Schuh et al. reported a POPF rate around 23% in stage D patients (main pancreatic duct diameter ≤ 3 mm, soft pancreas) but no data were available regarding major morbidity¹². Patients that will be considered eligible for the present trial will have further features increasing their risk of POPF and

related major morbidity, compared to stage D patients. Based on the current literature and on a recent retrospective study by the Verona group, considering only a cohort of patients with extremely high FRS (FRS 9-10), the rate of major morbidity can be estimated around 55% after PD and 19% after TP.¹¹

The original risk score proposed in this trial is extrapolated based on previous literature and expert opinions. For this reason, there are no data directly available for estimation of major morbidity in this rare subset of patients, for which we estimate a rate of Clavien-Dindo ≥ 3 of around 40%.

Considering a 1:1 allocation between the groups, a sample size of 49 patients per group would allow a two-sided, two-sample test for binomial proportions to detect a difference in Clavien-Dindo ≥ 3 of 25% (40% vs 15%) with 80% power ($1-\beta$) and an error α of 0,05. The study has a group sequential design allowing for interim analyses at pre-specified timepoints with possible early stopping for efficacy or futility in case of an overwhelming large or small effect, respectively. Considering that extremely high-risk cases represent around 7% of the total amount of PDs performed and that the fistula risk can only be assessed intraoperatively, we expect to approach preoperatively around 1300 patients.

STATISTICAL ANALYSIS

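### The denominator for access to adjuvant chemotherapy is set after surgery with no stated criteria, so patients with cancer who die early or are judged unfit can drop out of it and the arms' rates can be drawn together

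*Combined protocol and SAP*

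**What the plan says.** The Secondary Objectives include "To evaluate the access to adjuvant chemotherapy (when indicated", and the Secondary endpoints repeat the restriction: "Access to adjuvant chemotherapy (when indicated". The companion delay endpoint carries it too.

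The only statement of how the indication is set stands under Procedures, Postoperative care, after the description of the follow-up visits: "An oncologic evaluation will determine the indication for administration of adjuvant therapy, in case of malignancy". It gives no criteria for the evaluation and no date by which it must happen.

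The inclusion criteria admit "All patients scheduled for PD for all kind of pancreatic diseases", so only part of the sample will have a cancer that raises the question. The share is not stated.

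The introduction reports that "POPF is still associated with delays (> 8 weeks) or omission of adjuvant therapy in two-thirds of complication-bearing patient".

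The Statistical Analysis section offers a chi-square or Fisher's exact test for categorical variables. It does not say who is counted for this endpoint, how deaths or unfit patients are handled, or over what period access is measured.

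**The concern.** Randomisation protects a comparison only when the people counted are fixed by randomisation or by facts that treatment cannot change. Here the denominator depends on a judgement made after the operation, when complications and recovery are already known. A patient with cancer who dies before the evaluation has no indication on record. One who is septic or frail may be recorded as not indicated, when the informative entry would be indicated but not received. Either way a failure of access leaves the rate instead of counting against it.

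The trial is planned on the expectation that major morbidity differs between the arms, so these losses would be unequal. The arm with more complications would lose more of its failures, and the access rates would move towards each other. A real difference in the chance of receiving chemotherapy could then be reported as smaller than it is.

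**Working it through.** **The plan's own figure.** The documents give no planning figure for the access endpoint. The morbidity rates used below come from the sample size section, which plans to "detect a difference in Clavien-Dindo ≥ 3 of 25% (40% vs 15"%. A two-sided test of two proportions with pooled variance, alpha 0.05 and 80% power gives 49 per group, as stated (power at 49 is 80.1%). The present point does not depend on that figure.

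**Inputs.**
- c, major morbidity: 0.40 with anastomosis (PA) and 0.15 with total pancreatectomy (TP), from the sample size section. Applying these rates to the patients with malignancy is an assumption.
- m, share of complicated patients who miss chemotherapy because of the complication: assumed 2/3. This is an upper anchor, because the figure in the introduction combines delay with omission, and delayed patients do start.
- b, share not starting for unrelated reasons: assumed 10%.
- f, share of complication-related omissions classed as not indicated: unknown, varied from 0 to 100%.
- m, b and f are taken as equal in the two arms.

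**Formulas, per patient with malignancy.**
- Proportion starting: s = (1 − b)(1 − c·m)
- Proportion kept in the denominator: k = 1 − c·m·f
- Reported access: s / k

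**Everyone counted (f = 0).**
- PA: 0.90 × (1 − 0.40 × 2/3) = 0.90 × 0.733 = 66%
- TP: 0.90 × (1 − 0.15 × 2/3) = 0.90 × 0.900 = 81%
- Difference: 15 points

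**With reclassification.**

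| f | k, PA | k, TP | Access PA | Access TP | Difference |
|---|---|---|---|---|---|
| 0% | 1.000 | 1.000 | 66.0% | 81.0% | 15 points |
| 25% | 0.933 | 0.975 | 70.7% | 83.1% | 12 points |
| 50% | 0.867 | 0.950 | 76.2% | 85.3% | 9 points |
| 75% | 0.800 | 0.925 | 82.5% | 87.6% | 5 points |
| 100% | 0.733 | 0.900 | 90.0% | 90.0% | 0 points |

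**Sensitivity to m.** With everyone counted, the difference is 11 points at m = 1/2 and 7.5 points at m = 1/3. At f = 50% these become 6.5 and 4 points.

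**Patients involved at the extreme (m = 2/3, f = 100%).** If 60% of 49 per arm have malignancy (assumed), that is 29.4 per arm. Removed: 29.4 × 0.40 × 2/3 = 7.8 in PA and 29.4 × 0.15 × 2/3 = 2.9 in TP. For malignancy shares from 40% to 100%, the range is about 5 to 13 in PA and 2 to 5 in TP.

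**Power with everyone counted.** For 66% against 81%, the uncorrected two-sided test has about 25% power at 29.4 per arm, and 18% to 39% over the same range of malignancy shares. As a concrete case, 20 of 25 against 23 of 25 gives a Fisher p-value of 0.42.

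**The case against.** The strongest reply is that no passage makes fitness part of the indication. The evaluation is tied to malignancy and could be read as a matter of pathology alone. Since the trial enrols all pancreatic diseases, the restriction has an obvious innocent purpose: leaving out patients whose disease needs no chemotherapy. The introduction also speaks of omission, which treats complicated patients as candidates who missed treatment. All of this stands, and it means that loss from the denominator is possible, not established. It does not settle the point, because the pathology-only reading is not written down either, and a patient who dies before evaluation has no determined indication under either reading.

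A reader might infer that the plan removes the failures by rule and that the effect on access vanishes. The documents do not support that. They contain no such rule, and the difference reaches zero only if every complication-related omission is reclassified. Nor does the introduction support two-thirds as an omission rate, since it covers delay or omission together.

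It is also fair to say that a sound denominator would rarely change the test result, given the power shown above. Mortality and major morbidity are reported separately for each arm, so these patients do not disappear from the trial report. The primary endpoint is untouched.

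**Conclusion.** The point holds as a possible bias from a denominator that forms after randomisation without stated criteria. Its likely direction is towards no difference, as long as complicated patients are reclassified at similar rates in the two arms. With the planned morbidity rates, the upper-anchor omission share of two-thirds and 10% unrelated non-start, a 15-point difference shrinks to 12, 9 or 5 points at 25%, 50% or 75% reclassification. Zero is the worst case. Lower omission shares shrink both the true difference and the absolute loss. The omission share, the reclassification share, the unrelated non-start rate and the proportion with malignancy are all assumptions.

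This is a secondary endpoint with low power, so what is at stake is mainly the accuracy of an estimate. It should still be corrected, because the access result bears directly on the consequence of complications that the introduction describes.

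**What to change.** For the analysis, define the denominator by disease: all randomised patients whose final histology, and stage under a rule written in advance, make them candidates for adjuvant chemotherapy, whatever their postoperative course. A simpler alternative is all randomised patients with a resected malignancy. Count death, unfitness and refusal as no access within a stated time window, and record the reason for not starting. The oncologist's evaluation remains the care decision and supplies the recorded reason; nothing in patient management changes.

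The cost is a short addition to the endpoint definition and one case report form field. A histology-and-stage rule must cover all the diseases enrolled and be agreed by the lead centre and the at least two other international centres foreseen in the section on study duration. The resected-malignancy version avoids most of that work but includes some patients for whom chemotherapy would not be considered. With either version, access rates will look lower in both arms, and the report should explain why.

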Given the encouraging postoperative outcomes after TPs at high-volume centers, we conducted a retrospective analysis of all PDs and TPs performed at the Verona Pancreas Institute from July 2017 to December 2019 to evaluate TP as an alternative to PD in patients at high risk for POPF development.¹¹ Albeit the extensive application of the currently recognized mitigation strategies in the HR-PD group, including the use of externalized pancreatic stent and jejunostomy, patients who underwent TP exhibited comparable mortality (3% vs 4%, $p=0,6$) and strikingly better postoperative outcomes. In the HR-PD group, the rates of abdominal fluid collection, PPH, DGE, and LOS were nearly doubled, and the rate of sepsis was three times higher than those in the TP group. Major morbidity defined as Clavien-Dindo ≥ 3 was 1,5-fold higher in the HR-PD group (19% vs 31%; $p=0,05$). Additionally, cancer- and pancreas- specific QoL seemed to be comparable, while endocrine insufficiency and insulin-dependent diabetes occurred in the totality of patients after TP and TP was associated with worse diabetes-specific QoL. Furthermore, we identified a small cohort of patients (FRS 9-10) at extremely high-risk for POPF (60%) and major morbidity (55%).

This retrospective analysis suggests a role for TP after PD in selected patients at extremely high-risk for POPF after adequate counselling. For the sake of making progress in the management of the pancreatic remnant in high-risk scenario, we firmly believe that these findings need to be confirmed in a randomized fashion.

AIM OF THE STUDY

In patients at extremely high risk for POPF and related severe complications, TP may represent a potential rescue strategy to avoid the morbidity related to the pancreatic anastomosis.

The aim of the present study is to compare TP and primary pancreatic anastomosis (PA) in a cohort of extremely high-risk patients.

OBJECTIVES

PRIMARY OBJECTIVE

To evaluate whether TP is superior to PA in reducing major morbidity, defined as Clavien-Dindo ≥ 3 , in patients with extremely high-risk pancreas.

SECONDARY OBJECTIVES

- To evaluate the incidence and severity of general and pancreas-specific (POPF, postoperative pancreatitis, DGE, PPH, sepsis) postoperative complications and mortality in each group
- To evaluate time to functional recovery and length of hospital stay (days) in each group
- To evaluate the incidence and severity of postoperative endocrine and exocrine insufficiency in each group

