Continuous variables will be expressed as the means and standard deviation values or as median values with ranges and will be compared using the Student t-test or the Mann-Whitney test as appropriate. Categorical variables will be analyzed by Chi-square or Fisher's exact test in case of expected small frequencies. All the tests will be 2-tailed. P values < 0.05 will be considered statistically significant. All endpoints will require the above-mentioned statistical analysis, comparing the two study arms. Statistical analyses will be performed using STATA14 for Windows.

DURATION AND END OF THE STUDY

Since the Department of General and Pancreatic Surgery performs about 250 PD per year and the study will be proposed to at least other 2 international referral centers, the primary endpoint will be reached after 25 months: 22 months of patients' enrollment and 3 months of follow-up. Long term analysis of QoL and pancreatic insufficiency will require additional 24 month of follow-up. Time for data analysis must be considered negligible. All the patients undergoing PD will be enrolled for the study if inclusion and exclusion criteria will be respected. The study will be discontinued in case of reaching the statistical significance of the primary endpoint, or in case of suspension by the coordinators or by the authorities.

PROCEDURES RELATED TO REGISTRATION AND DATA MANAGEMENT

To ensure the confidentiality of data, each patient will be registered and de-identified by an identification code.

Each subject will be identified by a code consisting of:

- Code Protocol: TETRIS
- Number of the institution: (e.g. Patient recruited at the Verona Pancreas Institute will be coded as TETRIS_C1)
- Number of recruitment (e.g. the third patient recruited at the Verona Pancreas Institute will be coded as TETRIS_C1_3).

The P.I. of the study will be responsible for data protection and privacy of study participants by treating the data solely for statistical purposes and scientific research, and he will not communicate them if not anonymously. The manager of data processing is the principal investigator.

All data of enrolled patients collected during the study will be recorded in a computerized case report form (CRF) and transferred automatically into a specific database protected by passwords. These data will be kept confidential and will be treated in full compliance with the Legislative Decree 196/03.

ETHICAL CONSIDERATIONS

[figure not shown]

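### Delay to adjuvant chemotherapy exists only for patients who start, so the planned two-arm test of it compares groups formed after randomisation (minor, secondary endpoint)

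*Combined protocol and SAP*

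**What the plan says.** Under ENDPOINTS, Secondary endpoints, the protocol lists two items side by side: "Access to adjuvant chemotherapy (when indicated" and "Delay in starting adjuvant chemotherapy, calculated as the time between surgery and the beginning of adjuvant chemotherapy (when indicated". Access is also a stated secondary objective. Under Postoperative care, the indication is left to an oncologic evaluation after surgery in case of malignancy.

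STATISTICAL ANALYSIS says that continuous variables "will be compared using the Student t-test or the Mann-Whitney test as appropriate" and that categorical variables go to Chi-square or Fisher's exact test. It then adds: "All endpoints will require the above-mentioned statistical analysis, comparing the two study arms". For delay, no section names an analysis set, a cut-off, a censoring or ranking rule, or a way to handle death before chemotherapy.

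**The concern.** A t-test or Mann-Whitney test needs a number for each patient. Patients with an indication who never start have none, so they leave the comparison. Whether a patient starts is decided after randomisation and may depend on what happened after the operation.

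The protocol itself gives grounds for thinking so. Its background states that "POPF is still associated with delays (> 8 weeks) or omission of adjuvant therapy in two-thirds" of patients with complications. Its sample size targets a major morbidity difference of "25% (40% vs 15%) with 80% power". If complications lead to omission, and complications differ by arm, the starters in the two arms are no longer comparable. An arm could then look faster because its slower patients never started. Loss of adjuvant therapy is part of the trial's rationale, so this comparison will be read with interest.

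**Working it through.** **The plan's own figure.** The documents give no figure for the delay endpoint. The only stated sample size is 49 per group for 40% vs 15%. With pooled variance and two-sided 0.05:

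n = [1.96·√(2·0.275·0.725) + 0.8416·√(0.40·0.60 + 0.15·0.85)]² / 0.25² = (1.238 + 0.510)² / 0.0625 = 48.9, so 49.

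It is reproduced (power 80.1%), and nothing below changes it.

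**Inputs to the illustration.**
- From the documents: complicated patients p = 0.40 with pancreatic anastomosis (PA) and 0.15 with total pancreatectomy (TP). These are the planning rates for major morbidity.
- Assumed, not in the documents: mean delay 12 weeks (SD 3) if complicated and 7 weeks (SD 2) if not; 85% of uncomplicated patients start; a share q of complicated patients start; 30 patients per arm with an indication; cut-off 26 weeks.

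**Starters-only mean** = (p·q·12 + (1−p)·0.85·7) / (p·q + (1−p)·0.85). If every patient had a delay, the difference would be (0.40·12 + 0.60·7) − (0.15·12 + 0.85·7) = 9.00 − 7.75 = 1.25 weeks.

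| q, both arms | PA start | TP start | PA mean | TP mean | Difference |
|---|---|---|---|---|---|
| 0.30 | 63% | 77% | 7.95 | 7.29 | 0.66 |
| 0.50 | 71% | 80% | 8.41 | 7.47 | 0.94 |
| 0.70 | 79% | 83% | 8.77 | 7.63 | 1.14 |
| 0.85 | 85% | 85% | 9.00 | 7.75 | 1.25 |

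With q = 0.85, starting does not depend on complications and there is no distortion.

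**Reversal.** Let q = 0.85 in PA but 0.30 (0.50) in TP. The starters-only difference is 9.00 − 7.29 = 1.71 (9.00 − 7.47 = 1.53) weeks. TP looks faster than in the 1.25-week benchmark, although fewer TP patients start: 0.15·0.30 + 0.85·0.85 = 77% (80%) vs 85%.

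**Power by simulation, 30 per arm, no deaths.** The log-rank-type test keeps never-starters at risk to 26 weeks.

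| Scenario | Mann-Whitney, starters | Log-rank-type, all indicated |
|---|---|---|
| q = 0.30 | 9% | 28% |
| q = 0.50 | 14% | 21% |
| q = 0.70 | 20% | 16% |
| q = 0.85 | 24% | 12% |
| Reversal, TP q = 0.30 | about 39% | about 6% |
| Reversal, TP q = 0.50 | about 33% | about 7% |

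With no arm difference, both tests reject in about 5%. At 20 per arm the first four rows become 7/10/14/18% and 20/16/13/10%. Adding deaths of 4% (PA) and 3% (TP), the rates reported in the background, changes little: 9/13/19/23% and 26/22/16/12%.

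**Cumulative incidence of starting by 12 weeks** = p·q·0.5 + (1−p)·0.85·0.994. For q = 0.30/0.50/0.70/0.85 this gives PA 57/61/65/68% and TP 74/76/77/78%. The 95% half-width for the difference, 1.96·√[a(1−a)/30 + b(1−b)/30], is 22 to 24 percentage points. In the reversal with TP q = 0.30 the curves cross: PA vs TP is 68% vs 74% at 12 weeks and 85% vs 77% at 26 weeks.

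**The case against.** The strongest reply is that access and delay form a familiar two-part description: whether patients start, and when starters start. A reader would see any arm difference in starting from the access endpoint, and delay is one of many secondary endpoints. This justifies the low grade. It does not remove the point, because access shows how many are missing without correcting the delay test, which the plan still requires. The restriction to indicated patients does not help either: it says nothing about those with an indication who never start.

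Three stronger readings are tempting, and the documents do not support them.
- A reader might infer that starting is bound to differ by arm and that a TP advantage will be understated. The background gives no split between delay and omission, and it speaks of fistula, whereas the planning rates are for Clavien-Dindo ≥ 3.
- A reader might infer that TP causes omission through diabetes, since "endocrine insufficiency and insulin-dependent diabetes occurred in the totality of patients after TP". That passage reports the diabetes and says nothing about chemotherapy. The reversal is a possibility, not a forecast.
- A reader might take 1.25 weeks as the true effect. It assigns delays to patients who have none and serves only as a benchmark inside the illustration.

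It may also be objected that a Gray's test is not clearly better. That stands. It loses power when starting depends little on complications and has almost none when the curves cross. Where it gains most (q = 0.30), a plain Chi-square test of access already rejects in about 21%, so part of the gain re-tests access.

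**Conclusion.** The concern holds as a minor point on a secondary endpoint. That the planned delay test uses a group selected after randomisation follows from the text alone: the definition gives values only to starters, every endpoint must be tested between arms, and no rule covers the rest. Whether this biases the result, in which direction and by how much cannot be derived from the documents, and the bias may be zero. Every week and power figure above rests on assumed start rates, delays and numbers with an indication. The number indicated is itself unknown, because the trial enrols all pancreatic diseases. Precision will be low with any method, so estimates with intervals will tell more than a p-value.

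**What to change.** State in the analysis plan that access and timing are both analysed in all randomised patients with an indication, using one definition applied identically in both arms and one denominator for both endpoints. An indication read from the resection pathology is one option; it would define the analysis set only and leave the oncologic evaluation as it is. Report the cumulative incidence of starting chemotherapy from surgery by arm up to a cut-off fixed in advance. Keep never-starters at risk, treat death as a competing event, and give the between-arm difference with its 95% confidence interval. Report delay among starters descriptively beside access, without a between-arm test. A Gray's test may be added but is not required.

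The cost is a few lines of wording and at most one case report form item for the indication. Follow-up every 6 months for 2 years is already planned and covers a cut-off such as the 26 weeks assumed here. No visits are added and the sample size does not change. The downside is that the result mixes whether and when patients start, partly repeats access, and is no longer a simple mean delay.
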